9.3 General plan of statistical analysis

General principles of statistical analysis

All continuous variables will be summarised using descriptive statistics and represented as absolute numbers, sample size, arithmetic mean, standard deviation, median and percentiles, minimum and maximum values (depending on the type of distribution). The data on 3OT and on AR frequency will be presented as percentages of the entire population of patients enrolled in the study.

No inferential statistical analysis is planned as part of this uncontrolled study, since the design does not provide for comparison groups. The statistical analysis of the endpoints will be descriptive with testing of the null hypothesis, except for the statistical analysis of PK parameters, which will be compared with the pre-dose and post-dose values in several time intervals.

The source data are presented as tables, with individual study subjects listed in the rows and the values of the characteristic under investigation listed in the columns.

If the measured value of the characteristic under analysis in an individual study subject equals zero, the corresponding cell of the table shall contain the digit “0”.

All statistical calculations will be performed using the software package for statistical analysis R ver. 4.5.0 (2025-04-11 ucrt) and RStudio ver. 2025.05.1 “Mariposa Orchid”.

After study completion (after the last subject completes the study), a final statistical analysis of the results obtained is performed.

Analysis of baseline plan of the group

Perform analysis of the group by clinical and demographic parameters at the time of inclusion in the study. Use the methods of descriptive statistics to describe the baseline state in groups (for

quantitative parameters – n, arithmetic mean, median, standard deviation, minimum and maximum value; for categorical parameters – number and percentage).

9.4 Efficacy analysis

According to European guidelines (Guideline on the clinical investigation of human normal immunoglobulin for subcutaneous and/or intramuscular administration [SCIg/IMIg]), the number of patients greater than 40 has to ensure a minimum of 80 % statistical power for rejecting the null hypothesis when using a one-tailed test and a significance level of $p = 0.01$. For the primary efficacy variable, the null hypothesis H_0 is that the frequency of serious bacterial infection cases is 1.0 or greater per patient per year. The alternative hypothesis H_1 is that the frequency of serious bacterial infection cases is less than 1.0 per patient per year. The null hypothesis is rejected if the upper limit of the 99 % confidence interval is less than 1.0 case of serious bacterial infection per patient per year.

Secondary efficacy variables include the following parameters:

1. The threshold serum IgG level ≥ 5 g/L before the scheduled administration of the product (according to the PK study plan).
This variable is categorical, dichotomous, with categories of “response achieved” / “response not achieved”;
2. Cases of any non-serious infectious diseases during the treatment course, per patient per 1 year of therapy.
3. The duration of any non-serious infectious diseases during the treatment course, per patient per 1 year of therapy.
4. The fraction (%) of patients who were prescribed treatment with antibiotics.
5. The number of days of antibiotic therapy in a year (except for the cases where continuous antibiotic prophylaxis is performed).
6. Hospital admissions due to an infection (number of days and frequency in a year).
7. Fever episodes (number of events in a year).
8. The number of days of incapacity for work (sick leaves), or missing school/kindergarten due to an infection.
9. The quality of life level in the patients throughout the study period.

For quantitative variables, provide descriptive statistics in each group (n, arithmetic mean, standard deviation, median and percentiles, minimum and maximum values – depending on the type of distribution) for each visit according to the schedule of patient assessments. For the primary efficacy variable, the 95 % confidence interval, the absolute number, and the percentage of patients who achieved the efficacy endpoint are indicated.

Determine the relative changes in quantitative variables based on their mean values from the following formula:

$$X(\%) = \frac{T_i - T_{\text{baseline}}}{T_{\text{baseline}}} \times 100,$$

where T -baseline is the arithmetic mean of the variable at baseline, and T_i is the arithmetic mean of the analysed variable at subsequent visits. Represent these changes over time as a plot.

For variables measured only twice according to the schedule of patient assessments (at baseline and after completion of the course of treatment), evaluate the significance of their changes in each group using either a t-test for paired data or a Wilcoxon signed rank test, depending on the normality of the distribution, the latter checked with Shapiro–Wilk’s test.

For the variables measured according to the schedule of patient assessments more often than twice, evaluate the changes in quantitative variables over time using a one-way analysis of variance (ANOVA) or rank analysis depending on the normality of the distribution, checked using the Shapiro–Wilk test. In this setting, the dependent variable is the parameter being analysed, and the “visit” factor is the fixed parameter. Evaluate the value and significance for the reliability of the difference between the visits using a contrast analysis (simple contrasts) or post hoc analysis with Tukey’s test (for ANOVA) or the Wilcoxon signed rank test with Holm’s adjustment (for the rank test). To verify the preconditions for the use of analysis of variance, the normality of distribution of the residuals will be tested using the Shapiro–Wilk test. If the residuals are not distributed normally, a corresponding rank analysis will be performed.

Statistical inferences shall be made. For categorical variables, provide descriptive statistics (frequency and percentage [%]) and represent the distribution of categories in each group as a plot.

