9.6 Assessment of pharmacokinetic data

Analysis of pharmacokinetic parameters.

The main pharmacokinetic parameters include:

1. AUC-t value. Steady-state area under the concentration-time curve (AUC) for the total IgG level shall be compared with the values for the prior therapy (BIOVEN) for the relevant patient cohorts.
2. Trough IgG levels. The monthly trough IgG levels obtained, measured after 4 months of treatment with the IMP, prior to the next infusion, once every 4 weeks, over 6 months, shall be compared with the trough levels for at least two prior infusions of the previous SCIG or IVIG product. For treatment-naïve patients, a descriptive comparison with the data in published literature (if available) is required.

Methods of descriptive statistics: n, arithmetic mean, standard deviation, the median and the percentiles, the minimum and maximum values (depending on the type of distribution), including the plotting of graphs and charts and methods of interval estimation.

To evaluate the significance of changes over time in the event of assessing the parameter at two visits (before and after) in the case of quantitative variables, the analysis will use Student's t-test for paired data or Wilcoxon signed rank test – depending on the results of checking the normality of the distribution of difference [after - before] using the Shapiro-Wilk test. In order to assess changes over time in the event of measuring variables at more than two visits, methods of one-way analysis of variance (ANOVA) with subsequent application of post hoc analysis using Tukey's test will be used. In order to compare by those variables, by which the data were heterogeneous at baseline, covariance analysis (ANCOVA) will be used. In order to check the preconditions for the use of analyses of variance and covariance, the normality of distribution of the data and their residuals will be tested using the Shapiro-Wilk test. If the residuals are not distributed normally, or if the data do not pass the normality check, a corresponding rank analysis will be performed.

For the Shapiro-Wilk test, the significance level will be set at 0.01, and for other tests it will be set at 0.05. If a multiple comparisons effect occurs, significance level adjustments will be applied using the Holm method or Benjamini-Hochberg method.

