9.8 Levels of significance

The significance level for the Shapiro–Wilk test and for the primary efficacy variable shall be set at 0.01; for other statistical tests, it shall be set at 0.05.

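### The multi-visit ANOVA names visit as its only factor and no patient term, so it is conservative and can miss a small or moderate change over time

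*Protocol*

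**What the plan says.** Protocol section 9.4 covers quantitative variables assessed more often than twice. It tells the analyst to "evaluate the changes in quantitative variables over time using a one-way analysis of variance (ANOVA) or rank analysis", chosen by a Shapiro-Wilk test. The measured parameter is the dependent variable and the visit "factor is the fixed parameter". No patient factor, random effect or within-patient covariance is named. Visit differences are then judged by simple contrasts or Tukey in the ANOVA branch, or by the "Wilcoxon signed rank test with Holm" adjustment in the rank branch.

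Section 9.5 repeats this for laboratory values. Section 9.7 repeats it for IgG concentrations, without the simple contrasts. Section 9.6 prescribes, for more than two visits, "methods of one-way analysis of variance (ANOVA) with subsequent application of post hoc analysis" by Tukey's test.

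The variables concerned are repeated within patients. Monthly trough IgG values, taken "once every 4 weeks, over 6 months, shall be compared with the trough levels for at least two prior infusions" of the earlier product, exceed two visits. So do the blood tests and questionnaires in Table 4.2.1, and 9.4 lists "The quality of life level in the patients throughout the study period" as a secondary efficacy variable.

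For variables measured only twice, 9.4 does pair the data, "using either a t-test for paired data or a Wilcoxon signed rank test". Section 9.8 sets the level: "for other statistical tests, it shall be set at 0.05".

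**The concern.** A one-way ANOVA treats all measurements as independent. Here each patient contributes one value per visit, and patients differ persistently in IgG level, laboratory values and quality of life. With visit as the only factor, those stable differences go into the residual mean square, although they cancel when one visit is subtracted from another in the same patient. The estimated visit difference is unbiased, but its standard error is too large and the test rejects too rarely.

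The direction matters. Trough IgG is the primary pharmacokinetic endpoint, and objective 3 in section 3 is to show that troughs are not inferior to those on previous therapy. A test that loses power makes a modest decline harder to see. The same holds for a modest laboratory or quality-of-life change.

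The branches also disagree. If normality is accepted, multi-visit comparisons in 9.4, 9.5 and 9.7 use an unpaired error term. If it is rejected, the post hoc comparisons are paired signed rank tests. A check on distribution shape thus also decides whether those comparisons use the pairing.

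**Working it through.** **Inputs from the protocol.** Visit is the only factor (9.4, 9.5, 9.7). The level is 0.05 (9.8), taken as two-sided because sidedness is not stated. Troughs are measured in at least 40 patients (4.2), the pharmacokinetic group is 20 (9.7), and 56 are enrolled (9.2). The protocol gives no SD, within-patient correlation or detectable change for these tests, so there is no stated figure to reproduce.

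**Assumed inputs.** 7 visits; equal correlation rho unless stated otherwise; for the example, between-patient SD 2.0 g/L, within-patient SD 1.0 g/L and a linear fall of 0.8 g/L from first to last visit.

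**Step 1: the inflation factor.** With total variance s² and n patients:

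- one-way ANOVA: SE = sqrt(2s²/n)
- with a patient term: SE = sqrt(2s²(1 - rho)/n)
- ratio = 1/sqrt(1 - rho)

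| rho (assumed) | 0.3 | 0.5 | 0.7 | 0.8 | 0.9 |
|---|---|---|---|---|---|
| SE ratio | 1.20 | 1.41 | 1.83 | 2.24 | 3.16 |

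Simulation at n = 40 gave 1.22, 1.44, 1.86 and 3.20 for rho of 0.3, 0.5, 0.7 and 0.9.

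If correlation decays with time (AR(1)), the last-versus-first ratio over 7 visits is 1/sqrt(1 - rho^6). For lag-1 rho of 0.5, 0.7 and 0.9 this is 1.01, 1.06 and 1.46 (simulated 1.02, 1.08 and 1.49).

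**Step 2: the example by hand, n = 40.** Total variance = 4 + 1 = 5, so rho = 4/5 = 0.8.

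- One-way SE = sqrt(2 × 5/40) = 0.50. SE with patient term = sqrt(2 × 1/40) = 0.224.
- The Tukey multiplier for 7 visits (studentised range divided by sqrt 2) is 2.97 for both error degrees of freedom, 280 - 7 = 273 and 39 × 6 = 234.
- The observed fall must exceed 2.97 × 0.50 = 1.49 g/L without a patient term, or 2.97 × 0.224 = 0.665 g/L with one.
- The estimated fall has mean 0.8 and true SE 0.224. With the term, (0.8 - 0.665)/0.224 = 0.60, a power of about 73%. Without it, (0.8 - 1.49)/0.224 = -3.1, about 0.1%. Simulation, which lets the error variance vary, gives 0.3 to 0.6%.

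**Step 3: simulation of the same example.**

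| Test, n = 40 | As written | With patient term |
|---|---|---|
| Tukey, first vs last, fall 0.8 g/L | under 1% | about 73% |
| Overall F, linear fall 0.8 g/L | about 1% | 93 to 95% |
| Overall F, no change | 0.0% | about 5% |

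For Tukey, n = 20 gives about 0.1% against 32%, and n = 56 about 2% against 90%. An unadjusted simple contrast, which 9.4 and 9.5 allow, detects the fall in about 25% of trials, against about 94% for a paired t-test.

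**Step 4: sensitivity.**

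- *Size of fall.* At one total SD, sqrt(5) = 2.24 g/L, the one-way F test detects 100% and Tukey over 99% at n = 40. At 0.5 SD, the overall F test has power 0.32 against 0.86 (rho 0.5) and 0.08 against 1.00 (rho 0.9).
- *Shape of fall.* The overall-F result depends on shape. A step (three visits high, four low) gives 22% against over 99%.
- *Decaying correlation.* With AR(1) and lag-1 rho 0.8, Tukey detects 6% and an unadjusted paired t-test 44%. Part of that gap is Tukey's multiplicity adjustment.

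**The case against.** The strongest reply is that much of the plan is already paired. Two-visit variables get paired tests in 9.4, 9.5 and 9.6. Section 9.7 tests individual IgG differences from baseline with a paired t-test or signed rank test, whatever Shapiro-Wilk shows. The rank-branch post hoc tests are paired too. The primary pharmacokinetic endpoint is a mean trough over 6 months (4.1), which could be compared before versus after by a paired test. All of this stands. A reader might infer that Shapiro-Wilk decides whether pairing is used at all; the protocol supports that only for multi-visit comparisons. The reply is incomplete, because 9.7 goes on to prescribe the ANOVA for IgG and 9.6 prescribes it for more than two visits.

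A second reply is that repeated-measures ANOVA was meant and the SAP may say so. The protocol does not leave the model open, however: it names one-way ANOVA and its single factor, and writes pairing explicitly where it wants it.

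A third is that 9.3 says no inferential analysis is planned. Yet 9.4 and 9.5 call for statistical inferences and 9.8 sets a level for them.

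A fourth concerns consequences. A reader might infer that a non-significant ANOVA will be taken as proof that IgG is maintained or laboratory values are unchanged. The protocol states no such rule; 9.10 defines its non-inferiority conclusion on serious infections only. Nor are displayed error bars shown to be wrong: the plan reports SDs, medians and percentiles by visit, which this model does not touch. Laboratory values are also summarised as within or outside normal, and vital signs are descriptive.

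**Conclusion.** The point holds in a conditional form. As written, the ANOVA in 9.4 to 9.7 has the wrong error term for positively correlated repeats, and the error makes it conservative. The standard error of a visit difference is inflated by 1/sqrt(1 - rho) under equal correlation.

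A reader might take 1.4 to 3.2 as the size of the error in this trial. The protocol gives no correlation, so that range is only what rho of 0.5 to 0.9 would produce. At rho 0.3 the factor is 1.2, and for distant visits under decaying correlation it can be close to 1.

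A reader might also conclude that any real fall would be missed. Small or moderate falls can be, as in the 0.8 g/L example (0.8/2.24 = 0.36 total SD), but a fall of about one total SD is found with or without the patient term at 40 patients.

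Two-visit comparisons, the paired tests of IgG differences from baseline in 9.7, the rank-branch post hoc tests, the dichotomous IgG variable (5 g/L or more) and the primary serious-infection test are not affected.

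**What to change.** In 9.4, 9.5, 9.6 and 9.7, replace the one-way ANOVA by a repeated-measures analysis with visit as a fixed effect and patient as a term: either a mixed model with a random patient effect or a patient-blocked ANOVA. Follow it with multiplicity-adjusted within-patient contrasts. Name the Friedman test as the overall rank test, keeping the paired signed rank comparisons after it. Multi-visit comparisons are then paired in both branches, and the Shapiro-Wilk result no longer switches between unpaired and paired methods.

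Analysing IgG on the log scale, or using Holm rather than Tukey, is optional and not needed to cure the defect.

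The cost is amended wording in four sections, matching SAP text and a few lines of R. No new data, visits or patients are needed.

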9.5 Analysis of safety and tolerability parameters

a) Laboratory results (the indicators of complete blood count, serum chemistry and urinalysis). Compare the results of indicators at screening and at the last visit. Provide descriptive statistics for each laboratory indicator at time points T before treatment and T after treatment.

Determine the relative changes in quantitative variables based on their mean values from the following formula:

$$X(\%) = \frac{T_i - T_{\text{baseline}}}{T_{\text{baseline}}} \times 100,$$

where T_{baseline} is the arithmetic mean of the variable at baseline, and T_i is the arithmetic mean of the analysed variable at subsequent visits. Represent these changes over time as a plot.

For variables measured only twice according to the schedule of patient assessments (at baseline and after completion of the course of treatment), evaluate the significance of their changes in each group using either a t-test for paired data or a Wilcoxon signed rank test, depending on the normality of the distribution, the latter checked with Shapiro–Wilk’s test.

For the variables measured according to the schedule of patient assessments more often than twice, evaluate the changes in quantitative variables over time using a one-way analysis of variance (ANOVA) or rank analysis depending on the normality of the distribution, checked using the Shapiro–Wilk test. In this setting, the dependent variable is the parameter being analysed, and the “visit” factor is the fixed parameter. Evaluate the value and significance for the reliability of the difference between the visits using a contrast analysis (simple contrasts) or post hoc analysis with Tukey’s test (for ANOVA) or the Wilcoxon signed rank test with Holm’s adjustment (for the rank test). To verify the preconditions for the use of analysis of variance, the normality of distribution of the residuals will be tested using the Shapiro–Wilk test. If the residuals are not distributed normally, a corresponding rank analysis will be performed.

For each variable, plot the changes of mean values (when the distribution is normal) or median values (when the distribution is not normal) over time, for each group.

Convert the variables measured on a continuous scale into categorical variables with the following two categories: “within normal” and “outside normal”. Perform an analysis of the converted variables using the methods of descriptive statistics (the frequency and percentage [%] in each group have been provided) and represent the distribution of categories as plots. Statistical inferences shall be made.

b) The results of HR, BP, RR and body temperature measurements.

Calculate descriptive statistics (n, arithmetic mean, standard deviation, the median and the percentiles, the minimum and maximum values – depending on the type of distribution) for each visit according to patient assessment schedule.

c) AE data.

Provide descriptive statistics (frequency and percentage for the group).

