 - Paediatric patients are required to undergo Visits 1 and 2 of the screening period. In the event of meeting the criterion “total serum IgG level ≥ 5 g/L – as confirmed by the results of at least two (2) measurements performed immediately prior to the subsequent administration of IVIG after signing the ICF”, the patient proceeds to treatment with the IMP BP-SCIG 20%, starting from Cycle 1. If the criterion is not met, then Visit 3 is performed.

- Adult patients are required to undergo Visits 1 and 2 of the screening period to determine whether they meet inclusion/non-inclusion criteria, and Visit 3 of the screening period to conduct a mandatory pharmacokinetic assessment of BIOVEN.
- For Cohort C, newly diagnosed (treatment-naïve) patients are required to undergo Visit 1 of the screening period; if meeting inclusion/non-inclusion criteria, the patient proceeds to treatment with the IMP BP-SCIG 20%, starting from Cycle 1.

Study phases. Treatment period.

The phase begins after the end of the screening period.

Cycles 1–13: These include on-site visits to the CTS: 4 visits in Cycle 1; all subsequent cycles: each first visit of the cycle (every 28 days \pm 3 days) and interim self-administrations of the product by patients in the home (every 7 days \pm 1 day) for 52 weeks. A total of 13 cycles that include 13 main on-site visits (1 visit to the CTS in each cycle), and 3 on-site visits for interim administration of the IMP. The period lasts 52 weeks.

Individualised dose titration is performed.

A loading dose of IMP may be required (at the Investigator's decision): at least 0.2–0.5 g/kg (1.0–2.5 mL/kg) of body weight. This dose is distributed across several days, with a maximum daily dose of 0.1 to 0.15 g/kg.

After achieving a steady-state level of IgG, maintenance doses are administered at repeated intervals (approximately once a week) to achieve a cumulative monthly dose of 0.4–0.8 g/kg. Each single dose must be administered to different anatomical locations. (see Section 6.1 of this Protocol).

Pharmacokinetic parameters of the IMP are assessed at Week 21 (see Table 4.2.2)

Cycle 1:

- Visit 4 (C1W1): **On-site visit** Week 1 – the first administration of the IMP BP-SCIG 20%;
- Interim administration 1(C1W2) on-site – Week 2, administration of the IMP;
- Interim administration 2(C1W3) on-site – Week 3, administration of the IMP;
- Interim administration 3(C1W4) on-site – Week 4, administration of the IMP.

Cycle 2:

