The phase begins after the last administration of the IMP. It lasts 1 week after the last administration of the IMP.

- Visit 17: 1 week after the last administration of the IMP, the end of study.

At this phase, a set of laboratory tests is assessed and vital signs are measured. Registration of AEs/ARs is also performed.

The results of the study are entered into the eCRF, according to the Schedule of Study Procedures (see Table 4.2.1).

The procedures and phases are listed in Tables 4.2.1–4.2.3

Tabular schedule of study procedures

Table 4.2.1. Schedule of study procedures.

Visits	Visit 1	Visit 2	Visit 3	Cycle 1 Weeks 1–4			Cycle 2 Weeks 5–8			Cycle 3 Weeks 9–12			Cycle 4 Weeks 13–16			Cycle 5 Weeks 17–20			Cycle 6 Weeks 21–24		
Study phase	Screening period ∞						Treatment period														
Procedures / Time point	Day 0	Day 21–28	Day 42–56	Week 1 (C1W1)	Weeks 2–4 (C1W2-C1W4)	Week 5 (C2W5)	Weeks 6–8 (C2W6-C2W8)	Week 9 (C3W9)	Weeks 10–12 (C3W10-C3W12)	Week 13 (C4W13)	Weeks 14–16 (C4W14-C4W16)	Week 17 (C5W17)	Weeks 18–20 (C5W18-C5W20)	Week 21 (C6W21)	Weeks 22–24 (C6W22-C6W24)	Week 25 (C7W25)	Weeks 26–28 (C7W26-C7W28)				
Informed Consent signing	●																				
Collection of demographics	●																				
Collection of anthropometrics ¹	●	X	X	X	X	X	X	X	X	X	X	X	X	X	X	X	X	X	X	X	
Collection of medical history ²	●																				
Data on antibiotic therapy and concomitant therapy	●	●	●	●	●	●	●	#	●	#	●	#	●	#	●	#	●	#	●	#	
Presence of infections	●	●	●	●	●	●	#	●	#	●	#	●	#	●	#	●	#	●	#	●	
Physical examination ³	●	●	●	●			●		●	X		X			●		X				
Vital signs ⁴	●	●	●	●			●		●		●		●		●		●		●		
Chest X-ray/CT/MRI ⁵	X																				
12-lead ECG;	●																				
Complete blood count ⁶	●			●		●								●							
Serum chemistry ⁷	●			●		●								●							
Direct Coombs' test (antiglobulin test) ⁸	●	X	X	●		●		X		X		X		X		X		X			

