9.7 Analysis of pharmacokinetic parameters

Analysis of pharmacokinetic parameters in the respective group (n = 20) shall be performed by the variable of quantitative change of serum immunoglobulin IgG concentrations in patients (in grams per litre of blood) at protocol-specified time points.

For the aforementioned quantitative variable, provide descriptive statistics (n, arithmetic mean, standard deviation, the median and the percentiles, the minimum and maximum values—depending on the type of distribution) for each visit according to patient assessment schedule, and for the (Ti – T-baseline) differences.

Determine the relative change in the quantitative variable based on its mean values from the following formula:

$$X(\%) = (Ti - T_{\text{baseline}})/T_{\text{baseline}} * 100,$$

where T-baseline is the arithmetic mean of the variable at baseline (screening visit) and Ti is the arithmetic mean of the analysed variable at subsequent visits.

Plot graphs of changes of mean values over time (for normally distributed data) or changes of median values over time (for non-normally distributed data) for the variable.

Assess the significances of changes in these values in each group using Student's t-test for paired data or a Wilcoxon signed rank test depending on the normality of distribution of individual (Ti – T-baseline) differences, the latter tested using the Shapiro–Wilk's test.

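### Section 9.5 measures laboratory change from the Day 0 screening sample although the same tests are repeated at Week 1, so in Cohorts A and B about 3 to 12 weeks on the previous product enter the before/after comparison

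*Protocol*

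**What the plan says.** Section 9.5(a) of the protocol covers blood count, chemistry and urinalysis. Its opening instruction is "Compare the results of indicators at screening and at the last visit". The next one is "Provide descriptive statistics for each laboratory indicator at time points T before treatment and T after treatment", with no visit attached to either time point. In the relative-change formula the reference "is the arithmetic mean of the variable at baseline, and" again has no visit. For variables measured more than twice, the section adds an analysis of variance or rank analysis in which "the dependent variable is the parameter being analysed, and the “visit” factor is the fixed parameter", followed by simple contrasts or post hoc tests, and plots over time.

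The only place in Section 9 that ties baseline to a visit is 9.7, on IgG pharmacokinetics: "T-baseline is the arithmetic mean of the variable at baseline (screening visit").

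In Section 4.2, Table 4.2.1 marks the blood count at Visit 1, Week 1 and Week 5, and not at Visits 2 and 3. The chemistry and urinalysis rows show the same early pattern. Visit 4 (Week 1) is the first IMP administration. Patients in Cohorts A and B stay on their previous product during screening, and adults in Cohort B must also attend "Visit 3 of the screening period to conduct a mandatory pharmacokinetic assessment of BIOVEN".

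**The concern.** A before/after comparison of laboratory values is meant to describe what happens on BP-SCIG 20%. If the before value is the Day 0 sample, any change between Day 0 and the first IMP dose is counted as change on the IMP, or offsets a change that did occur on it. In Cohorts A and B that stretch is spent on another immunoglobulin product. There is no control arm in which such drift would show up and cancel.

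The length of the stretch differs between cohorts, so the same instruction means different things for different patients. A value from the visit of the first dose is already being collected, so nothing in the design forces the use of the older one.

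**Working it through.** **1. Which tests are drawn when.** Section 6.3.13 gives tube volumes: chemistry with IgG 5.5 mL, haptoglobin 3.5, Coombs 2, blood count 2, glucose 2, coagulation 3, glycated haemoglobin 4. The stated visit totals can be rebuilt from these:

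- Visit 1: 5.5 + 3.5 + 2 + 2 + 2 + 3 + 4 = 22 mL (stated 22).
- Visits 2 and 3: 5.5 + 3.5 + 2 = 11 mL (stated 11). This leaves no room for blood count or glucose.
- Visit 4: 5.5 + 3.5 + 2 + 2 + 2 = 15 mL (stated 15). Blood count and glucose are back.
- Visit 5: 15 + 3 = 18 mL (stated 18).

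The volumes agree with the schedule. For blood count and chemistry, the screening value is the Day 0 value, and a second pre-treatment opportunity exists at Visit 4. Urinalysis rests on the schedule alone.

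**2. Is the Visit 4 value taken before dosing?** The schedule says so explicitly only for IgG. Chemistry is listed in the same 5.5 mL volume as IgG, so pre-dose timing follows for it by inference. For blood count and urinalysis it is plausible but not stated.

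**3. The plan's own duration.** Section 4.5 gives screening up to 2 months, 52 weeks of treatment, 1 week of follow-up, and about 62 weeks in all. Taking 2 months as 61 days: 61/7 + 52 + 1 = 61.7 weeks, which reproduces 62.

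**4. Gap from the Day 0 sample to the first IMP dose.** The assumption is that the first dose follows directly after the last screening visit or sample. The interval from first dose to Visit 17 is 52 × 7 = 364 days. The share of the compared interval spent before the IMP is gap / (gap + 364).

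| Patients | Gap (days) | Weeks | Share |
|---|---|---|---|
| Cohort A, children in Cohort B, two screening visits | 21–28 | 3–4 | 5.5–7.1% |
| Same, with Visit 3 | 42–56 | 6–8 | 10.3–13.3% |
| Adults in Cohort B: Visit 3 plus BIOVEN sampling | 42 + 21 = 63 to 56 + 28 = 84 | 9–12 | 14.8–18.8% |
| Cohort C | Visit 1 only | – | no previous product |

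The largest share is 84 / (84 + 364) = 84/448 = 18.8%.

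**5. A conflict exposed by step 4.** With 12 weeks of screening the total is 12 + 52 + 1 = 65 weeks, not 62. Visit 3 as late as Day 56 followed by 28 days of mandatory sampling does not fit within 2 months. Sections 4.2 and 4.5 must be reconciled. Even at 61 days the gap would be 8.7 weeks.

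**The case against.** The strongest reply is that little depends on the sentence. Blood count, chemistry and urinalysis are measured more than twice, so 9.5 sends them to the by-visit analysis, where Week 1 is one of the levels and can be compared with the last visit. The paired test in 9.5 is reserved for variables measured only twice and so does not apply to them. The laboratory safety endpoint is the frequency of clinically significant deviations. Section 8.2 already counts abnormalities arising after IMP treatment starts and excludes those detected before the first dose. Adult cohorts are set at 8 to 10 patients out of 56, so the longest gap concerns few people. No decision rule uses this comparison.

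All of that stands, and it limits the point. It does not remove it. The protocol still orders a screening-versus-last-visit comparison, leaves the reference for the relative-change formula and the simple contrasts unnamed, and defines baseline elsewhere in Section 9 as screening. The comparison is written into the protocol, so it is not simply a detail left to the statistical analysis plan.

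Several stronger readings are tempting and are not supported:

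- A reader might infer that the Week 1 value goes unused. The by-visit analysis and plots include it.
- A reader might take 12 weeks as typical. It is the maximum, for adults in Cohort B with the latest Visit 3 and a 28-day BIOVEN interval.
- A reader might conclude that the results will be biased. Patients in Cohorts A and B have had at least 4 months of replacement therapy, and nothing in the protocol shows systematic drift between Day 0 and Week 1.
- A reader might point to blood sampling before the first dose in adult Cohort B. Adding the listed volumes gives 22 + 11 + 11 + 24.5 = 68.5 mL at the lower end. However, the 11 mL includes haptoglobin and Coombs tubes that are optional at Visits 2 and 3; without them the sum is 22 + 5.5 + 5.5 + 24.5 = 57.5 mL. No effect on any laboratory value is shown.
- A reader might want the baseline in 9.7 moved as well. That would be wrong: Sections 4.2 and 9.6 make IgG troughs on the previous product the intended comparator, and these are collected in screening.

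**Conclusion.** The point holds in a limited form. The named laboratory comparison in 9.5(a) runs from Day 0, and for Cohorts A and B it mixes change on the previous product with change on BP-SCIG 20%. The relative-change formula is open to the same reading. The off-IMP part is 3 to 12 weeks depending on cohort, at most 18.8% of the compared interval. Whether this shifts any reported mean cannot be told from the protocol. What is established is a misattribution of time.

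The effect is confined to descriptive safety output. The by-visit analysis, the adverse event counts under 8.2 and the primary efficacy test are not affected. It is worth correcting because the study has no control arm and the better value is already scheduled.

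The conclusion assumes that the early columns of Table 4.2.1 are read correctly from a partly misaligned table (the blood volumes support this for blood count and chemistry), that Visit 4 safety samples are or can be taken before dosing, and that dosing starts directly after screening. Any waiting time would lengthen the gaps.

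**What to change.** In 9.5(a), define the laboratory baseline as the last value before the first IMP administration: Visit 4 where measured, otherwise the latest screening value. Use it for the before/after comparison, for the relative-change formula, and as the reference visit for the simple contrasts. Keep Visit 1 values for eligibility; the change from screening to Week 1 can be tabulated separately.

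State in the schedule that the Visit 4 blood count, chemistry and urine samples are taken before dosing.

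In 8.1, tie the baseline used to judge laboratory deviations to the first-dose cut already applied in 8.2.

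Leave the screening baseline for IgG in 9.7 as it is. Reconcile the visit days in 4.2 with the screening and total durations in 4.5.

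The cost is a few sentences of text and one sampling-time instruction. No visits or samples are added.
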